**Study Protocol, Statistical Analysis Plan, and
Informed Consent**

Cover Page

NCT03567434

**Randomized, Double-Blind, Placebo-Based
Study to Determine Effect of Evening Alcohol on
Sympathetic Neural Activity and Baroreflex
Function in Binge Drinkers**

[figure not shown]
February 21, 2022

Study Protocol

Following enrollment in the study, participants were asked to complete one at-home, overnight sleep apnea test (ApneaLink, Resmed, San Diego, CA, USA) to screen for sleep-disordered breathing. If eligible following the at-home apnea testing (apnea-hypopnea index < 30 events/hour), participants were asked to report to the sleep laboratory at 9PM on a separate occasion to perform a familiarization overnight polysomnography (PSG) sleep study. This night was used to confirm the absence of sleep disordered breathing or other sleep disorders (i.e., restless leg syndrome, etc.) and to familiarize the participants with equipment and procedures.

After completing the familiarization night, participants were scheduled to return to the sleep laboratory on two occasions separated by one month. On each day of testing, meals throughout the day (i.e., breakfast, lunch, snack, and dinner) were provided based on participant caloric needs following consultation with a registered dietitian. Participants were assigned to a fluid control or alcohol condition separated by 1-month using a randomized, fluid-controlled, crossover design. Random assignment was performed by random selection of slips of paper with either experimental condition out of a cup by a blinded experimenter. In either condition, participants were asked to arrive to the laboratory at 4PM to assess breath alcohol concentration (Intoximeters, Inc., St. Louis, MO, USA) and hydration status via urine specific gravity (Schmidt Haensch, Berlin, Germany). During the alcohol condition, alcohol administration began at 8PM. Alcohol doses were diluted in a 1:3 ratio of 95% ethanol to fruit juice (orange or cranberry juice based on participant preference). A total dose of 1g/kg for males and 0.85g/kg for females was used. These doses were separated into a total of 6 aliquots, 3 of which were administered every 5 minutes starting at 8PM and another 3 starting at 9PM. In the fluid control condition, the same volume of fluid (i.e., juice) was ingested at each time point, but beverages did not contain alcohol but were masked with an alcohol mist. Participants were provided ad libitum water. The volume of fluid intake and urine output was monitored throughout the duration of the experimental visit. Following final dose administration, participants were instrumented with overnight PSG equipment. Following a venous blood draw and breathalyzer reading at 10PM for blood/breath alcohol concentration, participants entered bed at 10:45PM followed by lights out at 11PM. All participants were provided an 8-hour sleep opportunity.

Upon awakening at 7AM, participants' urine specific gravity was once again assessed, and another venous blood draw was performed to ensure that blood alcohol concentration had returned to baseline. Next, participants were asked to lie supine on a cushioned tilt-table for autonomic and cardiovascular testing. Recordings of beat-to-beat blood pressure via finger plethysmography (NOVA; Finapres Medical Systems, Amsterdam, The Netherlands), heart rate (HR; electrocardiography), respiration (pneumobelt), and muscle sympathetic nerve activity (MSNA) were established. After all autonomic and cardiovascular variables were obtained, participants rested for 10 minutes of non-recorded rest. Following this non-recorded period, three supine brachial blood pressures were taken using an automated sphygmomanometer (Omron HEM-907XL, Kyoto, Japan) after which 10-minutes of quiet, resting baseline data were obtained.

Statistical Analysis Plan

All data were analyzed using SPSS statistical software (Version 29.0, IBM Corp.). Shapiro-Wilk and skewness assessment were used to assess normality. Paired T-tests were utilized to assess differences in cardiovascular and sympathetic measures at rest. An α -value of 0.05 was used throughout.

Published Results

We have 21 peer-reviewed publications published so far related to this project:

Bigalke, J. A., Durocher, J. J., Greenlund, I. M., Keller-Ross, M., & Carter, J. R. (2023). Blood pressure and muscle sympathetic nerve activity are associated with trait anxiety in humans. *American journal of physiology. Heart and circulatory physiology*, 324(4), H494–H503. <https://doi.org/10.1152/ajpheart.00026.2023>

Bigalke, J. A., Cleveland, E. L., Barkstrom, E., Gonzalez, J. E., & Carter, J. R. (2023). Core body temperature changes before sleep are associated with nocturnal heart rate variability. *Journal of applied physiology* (Bethesda, Md. : 1985), 135(1), 136–145. <https://doi.org/10.1152/japplphysiol.00020.2023>

Bigalke, J. A., Greenlund, I. M., Nicevski, J. R., Tikkainen, A. L., & Carter, J. R. (2022). Sympathetic neural reactivity to the Trier social stress test. *The Journal of physiology*, 600(16), 3705–3724. <https://doi.org/10.1113/JP283358>

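### Does the lack of a PSG criterion for sleep-disordered breathing leave the population, and so the paired result, undefined?

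*Combined protocol and SAP*

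**What the plan says.** The Study Protocol describes two sleep screens before the experimental nights.

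- **Home test.** The condition for going on to the laboratory is numerical: "If eligible following the at-home apnea testing (apnea-hypopnea index < 30 events/hour".
- **Familiarization PSG.** The purpose is given as: "This night was used to confirm the absence of sleep disordered breathing or other sleep disorders". Getting participants used to the equipment and procedures is a second purpose. No PSG threshold or scoring rule is stated, and no step for a participant who does not pass.

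The next step is described by sequence: "After completing the familiarization night, participants were scheduled to return to the sleep laboratory on two occasions separated by one month".

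The Statistical Analysis Plan is short: "Paired T-tests were utilized to assess differences in cardiovascular and sympathetic measures at rest", with a significance level of 0.05 throughout. It defines no analysis set and no exclusions. In the text available, the population is otherwise named only in the title ("Function in Binge Drinkers"), with no list of inclusion and exclusion criteria.

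**The concern.** The two screens seem to apply different standards. A home limit of 30 events/hour admits people who have some respiratory events, whereas the PSG is there to confirm that sleep-disordered breathing is absent. Only the PSG could close the distance between those standards, and it has neither a definition of absence nor a stated consequence. Read literally, completing the night is enough to go on to the experimental visits.

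The topic bears on the outcomes, which are resting sympathetic and cardiovascular measures. The document's own publication list includes a title on sympathetic neural responses to sleep disorders. If people with sleep-disordered breathing were analysed and respond differently to alcohol, the mean paired difference would be an average over two kinds of participant in unknown proportion. A reader who took absence at face value would then apply the result to a population that was not the one studied.

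**Working it through.** The documents state no figure on this point other than the home limit, so there is nothing to reproduce. The check is a reading of the text, followed by a look at what the gap can do to the analysis.

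**1. Which populations does the text allow?** There are three readings:

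- (a) everyone with a home AHI below 30, with the PSG descriptive only;
- (b) those also below 30 on the PSG;
- (c) only those with no sleep-disordered breathing on the PSG, by an unstated cut-off.

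The home limit holds under all three, so the population is bounded. What is missing is its boundary with respect to sleep disorders inside that limit.

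**2. Do the statements contradict each other?** They do not. A lenient home screen followed by a laboratory check is a coherent sequence. The wording on the PSG states what the night was for; it does not report that every participant was found free of sleep disorders. The sentence about completing the night gives the order of events and need not mean that everyone advanced whatever the result.

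**3. Is the paired test affected?** Write participant i's outcome as a_i without alcohol and a_i + t_i with it. The paired difference is t_i. A stable trait such as sleep-disordered breathing, in so far as it shifts a_i, cancels. An exclusion based on the PSG is made before either experimental night and removes the person from both conditions, so it cannot unbalance the comparison. The test estimates the mean of t_i in those analysed, and it does so under (a), (b) and (c) alike.

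**4. What could differ between the readings?** Only the mean of t_i. Let D0 be the mean alcohol effect in participants without sleep-disordered breathing, p the share of analysed participants who have it, and r the ratio of their effect to D0. Then

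analysed mean = (1 − p) × D0 + p × r × D0,

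so the relative difference from D0 is p × (r − 1). The documents give neither p nor r. For illustration only, assume p = 5% to 30% and r = 0.5 to 2:

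| p | r = 0.5 | r = 2 |
|---|---|---|
| 5% | 0.05 × (−0.5) = −2.5% | 0.05 × 1 = +5% |
| 30% | 0.30 × (−0.5) = −15% | 0.30 × 1 = +30% |

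The result is zero if p = 0 or r = 1. The table restates its assumptions and is no evidence about this trial.

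**5. Would a repeat analysis without such participants help?** With a common SD of paired differences, its standard error would be larger by the factor 1/√(1 − p): 1.026 at p = 5% and 1.195 at p = 30%. A common SD does not fit with r different from 1, because mixing two effects widens the spread in the full sample. Take a within-group SD equal to D0, p = 0.30 and r = 2. The full-sample SD is then larger by √(1 + 0.3 × 0.7 × 1²) = √1.21 = 1.10, and the factor becomes 1.195 / 1.10 = 1.09. The cost therefore has no settled value. Nor can the analysis be specified, since it needs a definition the text does not give and participants who may not exist.

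**6. Would AHI by condition help?** It would be measured after the assigned beverage, so it cannot define a baseline population. The text also describes no respiratory scoring on the experimental nights.

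**The case for a change.** The strongest case for acting is that the plan spends a whole laboratory night on this check and then does not say how it was judged or what followed. The document is written in the past tense, so the answer should already be known. One or two sentences and a participant-flow line would settle it, and if nobody failed the PSG, saying so would be enough.

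The factual part stands: no PSG criterion, no consequence and no analysis set appear in the text. It also stands that a home limit of 30 events/hour is not the same standard as absence.

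The step from there to a defect in the plan does not. The ordinary reading of a night used to confirm absence is a screening step, and staff running it would treat it as one. The requested additions are a record of the criterion applied and counts of who passed, failed and was analysed. These belong to participant-flow reporting; they alter neither the design nor the test. Consent pages were removed from the document, so fuller eligibility criteria cannot be ruled out. If there were none, the PSG cut-off would be a small part of a wider silence on eligibility, and supplying it alone would still leave the population loosely described.

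**Conclusion.** No change to the plan follows. The screening description is incomplete on one detail, which those running the study would ordinarily fill by treating the PSG as a screen. The within-person comparison at the 0.05 level is sound however that detail was filled. The open question is one of applicability: whether the result describes people free of sleep-disordered breathing or, more broadly, people below 30 events/hour on the home test.

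The size of any difference between those two populations is unknown. It is zero if no affected participant was analysed or if the alcohol effect is the same in both groups, and the documents support no other figure. The conclusion rests on two conditions: any exclusion on the PSG was made before the experimental nights, as the order of the text implies, and not after outcomes were seen, which nothing in the text suggests. A report of the trial would do well to state the PSG criterion used, what happened to participants who did not meet it, and how many of them, if any, were analysed.

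### Do an all-juice control drink and free access to water undermine the fluid-controlled comparison?

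*Combined protocol and SAP*

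**What the plan says.** All of the drink details are in the Study Protocol section of the combined document.

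- **Alcohol drink:** "Alcohol doses were diluted in a 1:3 ratio of 95% ethanol to fruit juice". The dose is by body weight: "A total dose of 1g/kg for males and 0.85g/kg for females was used". It is split: "These doses were separated into a total of 6 aliquots", three from 8PM and three from 9PM.
- **Control drink:** "the same volume of fluid (i.e., juice) was ingested at each time point", and the "beverages did not contain alcohol but were masked with an alcohol mist".
- **Water:** "Participants were provided ad libitum water", with no distinction by condition.
- **Monitoring:** "The volume of fluid intake and urine output was monitored throughout the duration of the experimental visit". On arrival at 4PM the staff check "hydration status via urine specific gravity", and they repeat this on waking at 7AM.
- **Diet:** meals on each test day are supplied according to caloric needs, with dietitian input.

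The design is labelled a randomized, fluid-controlled crossover. The Statistical Analysis Plan section names paired t-tests on resting cardiovascular and sympathetic measures at α = 0.05. It does not mention the fluid, urine or specific-gravity data.

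**The concern.** A juice control of the same volume as an ethanol-juice mixture must contain more juice, and hence more sugar. That excess always goes with the control condition and scales with the dose. It is therefore in every within-person difference that the paired t-test averages, and randomizing the order does not cancel it. Free access to water also lets total fluid intake differ between nights, although the design is called fluid-controlled.

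If hydration or carbohydrate load shifted morning sympathetic activity or blood pressure, the contrast would no longer isolate alcohol. The plan collects the data that would show a fluid imbalance but does not say what is done with them.

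**Working it through.** The plan gives no juice volume, so there is no figure of its own to reproduce.

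**Inputs from the Study Protocol section:** ratio 1:3, 95% ethanol, 1 g/kg (men) and 0.85 g/kg (women), 6 aliquots.

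**Assumptions not in the documents:** ratio and strength by volume, ethanol density 0.789 g/mL, body weights as shown, juice sugar of 8 to 14 g per 100 mL.

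**Step 1. Juice ratio, by reading of the control-drink sentence**

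- Total volume matched, control all juice (the plainer reading): 4 parts against 3, so 4/3 = 1.33, or 33% more juice at equal drink volume.
- Juice volume matched: juice ratio 3/3 = 1, but total volume 3/4 = 0.75, so the control drink is 25% smaller.
- Total volume matched but ratio by weight (assumed densities 0.81 for the spirit, 1.04 for juice): juice per unit of spirit = 3 × 0.81/1.04 = 2.34 by volume. The ratio is 1 + 1/2.34 = 1.43, or 43% more juice.

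So the juice excess is 0%, 33% or 43%, depending on wording that the text leaves open.

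**Step 2. Size on the plainer reading**

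Spirit volume = dose × weight / (0.789 × 0.95). This equals the extra juice in the control drink.

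| | Ethanol (g) | Spirit (mL) | Juice, alcohol night (mL) | Juice, control night (mL) | Extra (mL) |
|---|---|---|---|---|---|
| Man, 80 kg | 80 | 106.7 | 320.2 | 426.9 | 106.7 |
| Woman, 65 kg | 55.25 | 73.7 | 221.1 | 294.8 | 73.7 |

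Per aliquot the extra is 106.7/6 = 17.8 mL and 73.7/6 = 12.3 mL. Over 50 to 100 kg it totals 67 to 133 mL for men and 57 to 113 mL for women. At the assumed sugar content that is about 5 g (57 mL × 0.08) to 19 g (133 mL × 0.14) for the evening.

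**Step 3. Timing**

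With three aliquots at five-minute intervals from 9PM, the last is at about 9:10PM. Waking is at 7AM, 9 hours 50 minutes later. Instrumentation and a further 10 minutes of unrecorded rest come before the resting data.

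**Step 4. What reaches the analysis**

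Write the paired difference (alcohol minus control) as D = τ − γ × (extra juice) + error, where τ is the effect of alcohol and γ the effect of each mL of juice on the morning measure. The bias is γ times about 57 to 133 mL. The documents give no value for γ and no evidence that it differs from zero after such an interval, so no bias can be computed.

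**Step 5. Water**

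Water drunk before 8PM precedes the drink. Water drunk after 8PM may respond to alcohol. That second part lies on a path from alcohol to the morning measures and belongs to alcohol's total effect. Free access permits a difference between nights but does not show one.

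**The case for a change.** The strongest case for acting is that the crossover offers no protection here. With juice as the only diluent and a ratio by volume, juice content and total volume cannot both be matched, so one of them differs on every pair of nights. Replacing the ethanol volume with water would have matched both. The investigators evidently thought fluid and diet mattered, since they supplied meals and recorded intake, output and specific gravity. A reader told that the design is fluid-controlled may fairly expect to see those data by condition.

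The geometry of this stands: on the plainer reading the juice difference is systematic. The reporting point also stands as a small one, because the SAP is silent on the fluid records. But that section is only four sentences long and names no covariates or descriptive tables of any kind. Setting out intake, urine output and 7AM specific gravity by condition is what an analyst would do with these records anyway.

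The remaining steps do not hold up. The protocol is written in the past tense and lists publications, so a different control drink could serve only later studies. It would also taste somewhat more dilute, which works against the masking. A model adjusted for water intake conditions on something that may follow from alcohol; it answers a different question and could remove part of the effect being studied. Renaming the design as matched on beverage volume is a matter of wording.

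**Conclusion.** No change to the plan follows. On the plainer reading the control carries about one third more juice, roughly 107 mL for an assumed 80 kg man and 74 mL for an assumed 65 kg woman. This rests on a ratio by volume, strength by volume and an ethanol density of 0.789 g/mL. Other readings give 0% (with a control drink 25% smaller) or about 43%, so one third is an inference and not a documented figure.

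Scheduled beverage volume is equal on the reading that produces the excess, so the label is defensible, though it covers less than total fluid intake. A juice difference of this size, nearly ten hours before waking and on days with supplied meals, is not shown to affect any analysed measure. The documents therefore do not support the claim that a morning difference cannot be attributed to alcohol. Unrestricted water is a fair trade-off: any response to alcohol remains part of its total effect, and the unadjusted paired comparison is the right one for that effect. What is left is missing reporting detail, which the recorded fluid and urine data allow analysts to supply descriptively.

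### Does the morning blood alcohol check need a stated limit and consequence, and do the fluid data need a stated use, before the paired comparison can stand?

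*Combined protocol and SAP*

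**What the plan says.** The Study Protocol gives a total alcohol dose of 1 g/kg (men) or 0.85 g/kg (women) in six aliquots, three from 8 PM and three from 9 PM. Before dosing, participants "arrive to the laboratory at 4PM to assess breath alcohol concentration" and urine specific gravity. Blood is first drawn at 10 PM, after dosing. At 7 AM specific gravity is repeated and "another venous blood draw was performed to ensure that blood alcohol concentration had returned to baseline". The text then moves straight to the recording: "Next, participants were asked to lie supine on a cushioned tilt-table for autonomic and cardiovascular testing".

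On fluids, the study is described as a "randomized, fluid-controlled, crossover design". In the control condition "the same volume of fluid (i.e., juice) was ingested at each time point". In addition, "Participants were provided ad libitum water", and "The volume of fluid intake and urine output was monitored throughout the duration of the experimental visit".

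The SAP is four sentences covering software, normality checks, the test and alpha. The test is described as follows: "Paired T-tests were utilized to assess differences in cardiovascular and sympathetic measures at rest". No analysis set, exclusion rule or covariate is named.

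**The concern.** The morning draw is presented as a safeguard, but a safeguard needs a criterion and a consequence, and neither is written down. The reference value is also unclear: the only alcohol reading described before dosing is from breath, while the morning sample is venous blood.

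Interpretation is at stake. If someone still had measurable alcohol when recording began, keeping that person would mix acute exposure with the morning-after effect. In a paired test, excluding that person's alcohol visit removes both visits. Only the alcohol visit can trigger the exclusion, so any losses would fall on slow eliminators. A reader of these documents cannot tell which course was taken.

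A second, smaller point is that fluid intake, urine output and specific gravity are collected under a design called fluid-controlled, yet water was unrestricted and the SAP gives these data no role.

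**Working it through.** The documents state no sample size, power, effect size or variance, so there is no figure of the plan's own to reproduce. Two questions can be examined: could a morning reading be above zero, and what would the missing rule change?

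**1. Is residual alcohol at 7 AM possible?**

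*From the Study Protocol:* doses of 1 and 0.85 g/kg; dosing starts at 8 PM and resumes at 9 PM, so 11 or 10 hours elapse to 7 AM.

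*Assumed, not in the documents:* distribution volume r of 0.60–0.75 L/kg (men) and 0.50–0.65 L/kg (women); constant elimination b in g/dL/h; full absorption.

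Starting concentration is C0 = dose / (10 × r) in g/dL:
- Men: 1/(10 × 0.75) = 0.133 to 1/(10 × 0.60) = 0.167.
- Women: 0.85/(10 × 0.65) = 0.131 to 0.85/(10 × 0.50) = 0.170.

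The residual is max(0, C0 − b × hours). It reaches zero by 7 AM if b is at least C0/hours:
- 11 hours: 0.0121–0.0152 (men), 0.0119–0.0155 (women).
- 10 hours: 0.0133–0.0167 (men), 0.0131–0.0170 (women).

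| b (g/dL/h) | Residual, 11 h, both sexes | Residual, 10 h, both sexes |
|---|---|---|
| 0.010 | 0.021–0.060 | 0.031–0.070 |
| 0.015 | 0–0.005 | 0–0.020 |
| 0.020 | 0 | 0 |

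A positive reading is therefore possible in slow eliminators, and the answer moves with the assumed clock. At b = 0.015 the maximum goes from 0.170 − 11 × 0.015 = 0.005 to 0.170 − 10 × 0.015 = 0.020.

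**2. How common might it be?**

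Simulation with r uniform over its range, b normal with a floor of 0.008, 11 hours from 8 PM, 400,000 draws per sex:

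| Mean (SD) of b | Above zero | Above an assumed 0.010 g/dL |
|---|---|---|
| 0.020 (0.002) | under 1% | under 1% |
| 0.018 (0.003) | about 8% | about 4% |
| 0.016 (0.003) | about 22% | about 14% |
| 0.015 (0.004) | about 36% | about 28% |

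Counting 10 hours from 9 PM raises the two middle rows to about 16% and 36% above zero. Recording starts after 7 AM, which works the other way: at 8 AM, 12 hours from the first dose, those rows fall to about 4% and 12%. The result is set by the assumptions.

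**3. What would the missing rule change?**

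Take an assumed 20 pairs, of which 2 or 4 are removed. For a standardised paired effect of 0.65, two-sided power from the noncentral t falls from 78.7% to 73.9% or 68.1%. In simulated trials at 80% power (effect 0.66 SD), keeping and excluding give different verdicts at 0.05 in 8.9% or 15.3% of trials. If the more favourable answer were chosen after the results were seen, the false-positive rate would be 6.4% or 7.2%.

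These last figures do not measure the stated harm. Pairs are removed at random and the true effect is the same in everyone, so the simulation contains no acute alcohol effect. It shows only what losing 10% or 20% of the pairs does to a paired t-test (2/20 and 4/20). The false-positive figure also needs a choice of rule made after seeing the results, which nothing in the documents suggests.

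**4. The fluid passages side by side.**

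Matched study drink, free water and recorded intake are compatible statements. Fluid-controlled reads naturally as a volume-matched drink, and the protocol already says that intake was monitored. Specific gravity has a stated measurement purpose, hydration status. Adjusting for fluid differences that arise after dosing could remove part of the effect of alcohol itself, so the data would at most be tabulated.

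**The case for a change.** The strongest case for a change is that the study's own wording makes clearance of alcohol a condition for interpreting the recording. A condition without a limit or a consequence cannot be verified. The event is plausible on reasonable kinetics and does not depend on trace values, since about 4–14% remain above an assumed 0.010 g/dL in the two middle scenarios. Disclosure would take a few sentences from data already collected.

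Much of this stands. The limit, the definition of baseline and the handling are absent, and a reader would be better served by knowing them. Three things keep it from being a defect in the plan:

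- The unclear analysis set is wider than this check. The SAP defines none, so a rule for the alcohol draw alone would leave missing visits and unusable recordings where they are.
- The documents are written in the past tense. A rule added now would be disclosure and not pre-specification, and it would have to report the definition actually applied, not one supplied by a reviewer.
- A comparison with and without the affected participants would be descriptive and would not gate the conclusion. If every sample had returned to baseline, nothing would differ.

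**Conclusion.** No change to the plan follows. This is a gap that an analyst can fill sensibly from the stated intent: alcohol was meant to have cleared before the recording, and any visit where it had not would be reported along with how it was handled. No stated rule produces a wrong estimate or test, and no affected participant is shown.

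The possible size is undetermined. With 11 hours counted from 8 PM, the share above zero at 7 AM is under 1% to about 36%, depending entirely on assumed elimination and distribution values; the sample size is not stated. The verdict-change and false-positive figures should carry no weight, for the reasons shown in the working.

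The fluid point does not hold as a contradiction. A table of fluid intake, urine output and specific gravity by condition would be an optional reporting courtesy and would alter no result.

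### The two-visit crossover is analysed by paired t-test with no period term, so a visit-1 to visit-2 shift costs precision and, with unequal orders, also moves the alcohol estimate

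*Combined protocol and SAP*

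**What the plan says.** The Study Protocol describes a crossover: "Participants were assigned to a fluid control or alcohol condition separated by 1-month using a randomized, fluid-controlled, crossover design". There are two experimental visits: "participants were scheduled to return to the sleep laboratory on two occasions separated by one month". Order was set by lot: "Random assignment was performed by random selection of slips of paper with either experimental condition out of a cup by a blinded experimenter". The text does not say whether slips were replaced, whether the two kinds were equal in number, or how many participants ended in each order.

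The Statistical Analysis Plan is four sentences: software, normality checks, the test, and an alpha of 0.05. The test is given as "Paired T-tests were utilized to assess differences in cardiovascular and sympathetic measures at rest". No period, sequence or order term appears anywhere.

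Two features of the Study Protocol may reduce a visit effect. One purpose of the familiarization night was "to familiarize the participants with equipment and procedures". Before each recording, "participants rested for 10 minutes of non-recorded rest".

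**The concern.** In a two-period crossover each participant's alcohol-minus-control difference also contains a visit-2 versus visit-1 difference, with opposite signs in the two orders. Habituation to the laboratory or the recording set-up could produce such a shift, as could drift over the month. A paired t-test pools the differences without regard to order. The shift therefore adds to their spread and cancels from the mean only if the orders are equal in number.

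At stake is how the reported effect can be read. From these documents one cannot tell whether an alcohol effect on resting blood pressure or sympathetic activity includes part of a visit effect, because neither the order split nor an adjusted estimate is planned. The trial should already hold the order data that would settle this.

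**Working it through.** **Inputs.** From the documents: two conditions, two visits, order by lot, paired t-test, alpha 0.05 (taken as two-sided). The documents state no power or sample-size figure, so there is none to reproduce. Assumed: n = 20 (range 12 to 30), and a true effect giving the paired t-test 80% power when there is no shift (0.89, 0.66 and 0.53 SD at n = 12, 20 and 30). All effects and shifts are in SDs of the within-person difference.

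**Model.** Let τ be the alcohol effect and δ the visit-2 minus visit-1 shift. The alcohol-minus-control difference has mean τ + δ in control-first participants and τ − δ in alcohol-first participants.

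- The paired t-test estimates τ + δf, where f = (n control-first − n alcohol-first)/n.
- Its SE is inflated by about √[1 + δ²(1 − f²)·n/(n − 1)].
- The period-adjusted estimate is the average of the two order-specific mean differences. It is free of δ and has n − 2 degrees of freedom. Its SE is larger by √[n²/(4·n₁·n₂)] when the orders are unequal.

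**Chance of imbalance at n = 20**, if each participant's order was an independent 50:50 draw (an assumption): exactly equal 18%; 7:13 or worse 26%; 6:14 or worse 12%.

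**Results by fixed split at n = 20** (simulation, 100,000 runs per case for 10:10, 7:13 and 6:14):

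- **10:10, δ = 0.25.** No bias. CI 3% wider; power 78% paired, 80% adjusted.
- **10:10, δ = 0.5.** No bias. SE factor √(1 + 0.25 × 20/19) = 1.12, so the CI is 12% wider. Type I error 3.0%; power 72% paired, 80% adjusted.
- **8:12.** Bias 0.25 × 4/20 = 0.05 SD at δ = 0.25 and 0.5 × 4/20 = 0.10 SD at δ = 0.5. Type I error 4.9% and 4.5%: the wider SE offsets the bias in the error rate, but the estimate is still moved.
- **7:13, δ = 0.25.** Type I error 5.4%.
- **7:13, δ = 0.5.** Bias 0.5 × 6/20 = 0.15 SD. Type I error 6.5%; 95% CI coverage 93.5%. Power is 89% or 49% depending on the direction of the imbalance, against 76% adjusted.
- **6:14.** At δ = 0.25, type I error 6.3%. At δ = 0.5, bias 0.5 × 8/20 = 0.20 SD, type I error 9.7%, coverage 90.3%.

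**Averaged over the draw at n = 20.** Paired power is 80%, 78%, 71% and 61% at δ = 0, 0.25, 0.5 and 0.75. Adjusted power does not depend on δ and is about 77.5% throughout. The paired test's type I error stays near 5%.

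**Break-even shift** above which adjustment has the higher average power: about 0.36 SD at n = 12, 0.25 at n = 20 and 0.20 at n = 30. With equal orders at n = 20 it is about 0.1 SD.

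**The case against.** The strongest reply is that no shift is shown to exist and that the paired t-test is sound under randomization: unbiased over the draw, with about 5% error. The protocol also standardizes much that could drive a visit effect. Beyond the familiarization night and the rest period, meals were provided, arrival, lights-out and waking times were fixed, and hydration was checked. At n = 20 about 74% of draws are 8:12 or better balanced, and there the false-positive rate stays at or below about 5% at the shifts examined. If there is no shift, adjustment loses power: about 77.5% against 80% on average, and about 73% against 80% at a 6:14 split. A realised order split would not normally appear in a plan, and the listed paper on morning sympathetic activity may report one.

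Most of this stands, and it limits the weight of the point. The raised error rates need both a sizeable shift and a less likely split. It does not remove the point. Standardization may shrink a shift but does not adjust for what remains. The Study Protocol describes the familiarization session as an overnight sleep study and does not say that nerve recording or the tilt-table session was rehearsed. Equal orders would remove the bias but not the loss of precision. Validity averaged over draws does not protect the estimate from the one split that occurred. Nothing can be said here about what the listed paper reports; the claim concerns only what these documents plan.

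**Conclusion.** The concern holds as a cheap improvement, held with moderate confidence. The missing period term is plain from the text, and the mechanism is algebra. The paired t-test is not invalid, and no reported conclusion is shown to be wrong.

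The practical size is unknown. At an assumed 20 participants, a shift of 0.25 SD does little unless the split is poor. A shift of 0.5 SD costs about eight points of power with equal orders, and about seven on average over the draw. At splits of 7:13 or worse it moves the estimate by 0.15 SD or more. These figures rest on the assumed sample size, effect and shift; the split probabilities also assume independent 50:50 draws.

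**What to change.** Add a period-adjusted analysis of each resting measure: a mixed model with condition, period and sequence as fixed effects and participant as random. With complete pairs the equivalent is an independent-samples t-test comparing the visit-1 minus visit-2 difference between the two order groups. Half the difference in means, taken as alcohol-first minus control-first, is the alcohol effect, and half the CI limits are its limits. Report the estimate with its 95% CI and the number of participants in each order.

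The plan is in the past tense ("All data were analyzed using SPSS statistical software"), so this cannot be presented as prospective. Label it a re-analysis and show it beside the paired t-test, which remains the stated analysis.

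The work is one added sentence and one re-run in the same software. The statistical price is one degree of freedom plus a larger SE when orders are unequal: √(400/364) = 1.05, or 5%, at 7:13; √(400/336) = 1.09, or 9%, at 6:14; and √(144/108) = 1.15, or 15%, at 3:9 if n = 12. With equal orders and no shift, power at n = 20 is essentially unchanged. Below the break-even shift the paired test is the more powerful on average, which is the reason to show both.
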